## Consent to participation and feedback of results

- The conduct of this study will be in accordance with the principles of Good Clinical Practice. All potential participants will be offered a patient information leaflet as well as a copy of the consent form. Participants will be made aware that they can withdraw from the trial at any stage and have their information destroyed.
- Patients will be informed of the results of their genital infection screen and appropriate treatment will be provided as necessary as per Birmingham Women's Hospital antimicrobial prescribing guidelines.
- Patients will also be informed if their pregnancy test performed prior to HyCoSy is positive as they will no longer be able to take part in the study.
- HyCoSy findings will also be shared with the participants at the time of the scan. Any HyCoSy findings that may require urgent gynaecological attention will be referred to the on call gynaecology team at the Birmingham Women's Hospital with the patient's consent. Any other ultrasound findings that require non urgent follow up, will be shared with the GP or routine healthcare provider, with the patient's consent.

## Dissemination of study results

The results of the study in terms of the prevalence of hydrosalpinges in the recurrent miscarriage population and the prognosis of women with recurrent miscarriage and concurrent hydrosalpinx will be disseminated to all participants via an email newsletter at the conclusion of the study. The results of comparing outcomes between patients who were treated for their hydrosalpinges versus those who were not, will be also be disseminated to all study participants and those who were not treated will be offered discussion about treatment after the conclusion of the study if treatment shows significant benefit.

## Withdrawal process

Participants will be informed that they are able to withdraw from the study at any point without giving a reason and without any impact on their care, however, information gathered up until that point may be still used in the study.

## Patient Journey

The patient will be sent the patient information leaflet at the same time as they receive the appointment letter thus ensuring sufficient time to read the written information related to the study before consent is taken. Written informed consent will be taken by good clinical practice trained research midwives or [name], a General Medical Council and Royal College of Obstetricians and Gynaecologists registered registrar who is fully competent at taking consent and is also good clinical practice trained.

If a patient consents to participation, they will have the swabs performed as detailed in the method of collection of data and outcomes section above. If the swabs show an infection this will be treated

as per the Birmingham Women's Hospital microbiology prescribing guidelines. At a subsequent appointment they will have a HyCoSy to detect the hydrosalpinges instead of their usual transvaginal pelvic ultrasound scan. A HyCoSy, as detailed in the background section above, incorporates a transvaginal ultrasound scan but is more detailed due to the use of contrast media to detect tubal and uterine pathology which may not be visible on normal transvaginal ultrasound. The result of which will be fed back to the patient and their usual clinician. They will then discuss with this clinician any treatment that maybe required.

If a hydrosalpinx is detected they will discuss with their usual clinician whether tubal surgery and what type would be appropriate. Surgery would then be carried out in the usual manner by the usual clinician. All patients would now be in one of three groups, those with no hydrosalpinx, those with a hydrosalpinx who did not have surgical treatment and those with a hydrosalpinx who did have surgical treatment of their hydrosalpinx. All three cohorts will then be followed up for 12 months as detailed in the method of collection of data and outcome section above. A pictorial representation of the patient journey is shown below in the study flow chart section.

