## Outcomes to be measured

- To establish the second objective of prognosis of women with recurrent miscarriage and concurrent hydrosalpinges, pregnancy outcome data will be collected from both groups of patients (patients who screen positive and those who screen negative for hydrosalpinges). Specifically this will include:
  1. Biochemical pregnancy – a positive pregnancy test either on urine or serum pregnancy testing before ultrasound evidence of a gestational sac
  2. Clinical pregnancy – a pregnancy confirmed by evidence of a fetal heartbeat on ultrasound scan or using ultrasound parameters (ultrasound visualization of a gestational sac, embryonic pole with heartbeat).
  3. Pregnancy loss and at what gestation the pregnancy was lost – if unfortunately the patient suffered from a further miscarriage or still birth, the gestation in weeks of the loss will be noted
  4. Ectopic pregnancy – if a clinical pregnancy is seen on ultrasound scan but its location of implantation has taken place outside the uterine cavity, this is known as an ectopic pregnancy. Ectopic pregnancies are usually inside the fallopian tube although rarely they can be abdominal, ovarian or cervical.
  5. Live births – if fortunately a patient has a live birth this will be noted.
- To explore the role of tubal surgery, the same pregnancy outcomes listed above will be collected for the group of patients that were treated by their usual healthcare provider with surgery for their hydrosalpinges.

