## Method of collection of data and outcomes

- The genital infection screen will be performed by taking a self-taken vulvovaginal swab and a high vaginal swab after written informed consent has been gained. The high vaginal swab will be taken by [name], a General Medical Council and Royal College of Obstetricians and Gynaecologists registered registrar who is fully competent in such a procedure.
- The presence or absence of hydrosalpinges will be noted at HyCoSy which will be performed after recruitment and written informed consent has been gained. A urine pregnancy test will also be performed prior to the HyCoSy to ensure the patient is not unknowingly already pregnant which would exclude them from the study. The HyCoSy and pregnancy test will be performed by [name], a General Medical Council and Royal College of Obstetricians and Gynaecologists registered registrar who is fully competent in such a procedure.
- The pregnancy outcome data listed above will be collected via a telephone consultation or email correspondence, conducted at 6 months and 12 months either post HyCoSy or post

treatment. Should the patient not recall all of the information needed, she will be consented to examine her hospital patient records. Should the patient have had treatment at a different hospital trust, she would also have been consented to collect the specific information needed directly from that particular hospital's patient records.

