### Statistical Analysis

For the prevalence survey of hydrosalpinx in the recurrent miscarriage population data will be presented using descriptive statistics. We will examine the prevalence data within subgroups created from clinical characteristics for example age, body mass index, previous sexually transmitted infections to identify high risk groups for hydrosalpinx.

For the comparison of the cohorts we will report numbers of individuals at each stage of study e.g. numbers potentially eligible, examined for eligibility, confirmed eligible, included in the study, completing follow-up, and analysed. The reasons for non-participation at each stage will be described. We will also describe the characteristics of study participants (e.g. demographic, clinical) and potential confounders (e.g. age, body mass index.) We will indicate the number of participants with missing data for each variable of interest and compute data for missing covariates using maximum likelihood estimation. We will summarise follow-up time (e.g. average and total amount) and report numbers of outcome events over time for each cohort. We will report unadjusted relative risk estimates and, if applicable, confounder-adjusted estimates and their precision (e.g. at the 95% confidence interval). We will endeavour to translate estimates of relative risk into absolute risk for a meaningful time period. Subgroup analyses will be also performed according to the risk stratification described above.

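### Women with hydrosalpinx are grouped by whether surgery later took place, so conceptions during the wait bias the exploratory per-woman surgery comparison

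*Protocol*

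**What the plan says.** In the protocol's Patient Journey section, a woman with hydrosalpinx discusses surgery with her usual clinician after HyCoSy, and any surgery is then carried out. Only after that are the cohorts named: "All patients would now be in one of three groups, those with no hydrosalpinx, those with a hydrosalpinx who did not have surgical treatment". Operated women form the third group. The section continues: "All three cohorts will then be followed up for 12 months". It gives no interval to surgery and does not say how a conception before surgery is classed.

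Method of collection of data and outcomes sets the contacts as "conducted at 6 months and 12 months either post HyCoSy or post" treatment, without tying either origin to a cohort. Patient Journey adds: "A pictorial representation of the patient journey is shown below in the study flow chart section". That chart is not reproduced in the text available for this review.

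Outcomes to be measured says that the same pregnancy outcomes "will be collected for the group of patients that were treated by their usual healthcare provider with surgery for their hydrosalpinges". For a loss, "the gestation in weeks of the loss will be noted"; for a live birth, only "if fortunately a patient has a live birth this will be noted". Statistical Analysis will "report numbers of outcome events over time for each cohort" and give relative risks, unadjusted and, where applicable, adjusted for confounders, with age and body mass index as examples. Dissemination of study results sends the treated-versus-untreated comparison to all participants. If treatment proves significantly beneficial, untreated women are offered a discussion about it.

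**The concern.** Membership of the two hydrosalpinx groups is decided by what happens after HyCoSy. An operated woman has reached surgery without an ongoing pregnancy that prevented it. A woman planned for surgery who conceives first, and so is not operated on, moves to the unoperated group and brings her pregnancy with her. The unoperated group is thereby enriched with conceptions even if surgery does nothing. Adjusting for age or body mass index does not undo this, because the selection is on the outcome itself.

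The direction depends on the outcome. Per woman, the unoperated group gains conceptions, live births and losses alike. A real benefit of surgery on conception or live birth could be hidden, while a benefit on miscarriage per woman could appear where none exists. The protocol does not fix the denominator for loss. The comparison at stake is the one that participants will be sent and that may prompt a discussion of treatment.

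**Working it through.** **Plan's own figures.** The protocol gives no figure for the surgery comparison, so there is none to reproduce. The relevant numbers are the recruitment target of 203 and the prevalence ceiling of 25% (Sample Size): 0.25 × 203 = 50.75, at most about 51 women with hydrosalpinx.

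**Assumed inputs, none in the protocol.** 12-month conception probability when trying, p = 0.60, at a constant rate; wait to surgery w = 3 months; share planned for surgery s = 0.5; share q of planned women trying while waiting; any conception during the wait cancels surgery; no surgery effect. All other women try from HyCoSy, and operated women try from surgery.

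**Natural reading: operated women followed from surgery, the rest from HyCoSy.**

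1. Conception during the wait if trying: c = 1 − (1 − p)^(w/12) = 1 − 0.4^0.25 = 0.205.
2. Unoperated risk: [(1 − s)p + s·q·c] / [(1 − s) + s·q·c].
3. Operated risk: p = 0.600.

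| Case | Unoperated risk | RR |
|---|---|---|
| All try (q = 1) | (0.300 + 0.102)/(0.500 + 0.102) = 0.668 | 0.600/0.668 = 0.90 |
| A quarter try (q = 0.25) | (0.300 + 0.0256)/(0.500 + 0.0256) = 0.620 | 0.97 |
| None try (q = 0) | 0.300/0.500 = 0.600 | 1.00 |
| w = 6, s = 0.75, all try (c = 1 − 0.4^0.5 = 0.368) | (0.150 + 0.276)/(0.250 + 0.276) = 0.810 | 0.74 |

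**Other outcomes, base case with all trying.** If every woman has the same loss risk (say 35%) and pregnancies are followed to their end:

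- Loss per woman: 0.35 × 0.600 = 0.210 against 0.35 × 0.668 = 0.234, RR 0.90.
- Live birth per woman: the same ratio, 0.90.
- Loss per pregnancy: 0.35 in both groups, RR 1.00.

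If only births within the 12-month window count, and birth comes 8.5 months after conception (assumed), conception must fall in the first 3.5 months: 1 − 0.4^(3.5/12) = 0.235.

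- Operated: 0.65 × 0.235 = 0.153 (from unrounded values).
- Unoperated: 0.65 × (0.5 × 0.235 + 0.5 × 0.205)/0.602 = 0.237.
- RR 0.64, so a strict 12-month cut-off makes the live-birth distortion larger.

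A simulation of the same case, counting losses only within the window, gives 0.87 for loss per woman.

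**Everyone followed for 12 months from HyCoSy, still grouped by later surgery.** Operated women cannot have conceived in the first 3 months: 1 − 0.4^(9/12) = 0.497. RR = 0.497/0.668 = 0.74 if all planned women try while waiting, and 0.497/0.600 = 0.83 if none do. A common clock alone does not remove the bias.

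**Precision.** With 25 women per group and a 30% risk, the SE of log RR is √[2 × (1/7.5 − 1/25)] = 0.432, so a null 95% CI runs from about 0.43 to 2.33. At an assumed 10% prevalence (about 20 women, 10 per group), the SE is √[2 × (1/3 − 1/10)] = 0.683 and the CI about 0.26 to 3.81. On the first of these, an RR of 0.90 is |ln 0.90|/0.432 = 0.24 SE from the null, and 0.74 is about 0.70 SE.

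**The case against.** The strongest reply is that the follow-up origin is hardly in doubt. Only operated women have a post-treatment date, and Patient Journey runs in order from HyCoSy to surgery to grouping to follow-up. A reader might infer that the protocol leaves the clock wide open. It does not: the natural reading is surgery for operated women and HyCoSy for the rest, and the flow chart may say so. What stands is that the text does not state it, and that settling it leaves the grouping problem in place.

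A reader might also infer that losses between HyCoSy and surgery are counted in neither cohort. The documents do not support that. Method of collection of data and outcomes times the contacts, but does not say that outcomes asked about at a post-treatment contact begin at surgery. Outcomes to be measured covers all women who screen positive, and records may be consulted. Such losses may well be captured; the protocol should say so.

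Third, the bias needs women to conceive while waiting, and the protocol gives no waiting time, surgery share or proportion trying. That is right, and is why the null RR ranges from 1.00 downwards. Fourth, the comparison is exploratory and random error will dominate. That also stands, and limits the weight of the point.

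Finally, time-dependent methods can be left to a statistical analysis plan. The method can, but the data cannot: no later plan can reliably split pregnancies or time at surgery if the dates were never collected. The protocol lists gestation for losses only.

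**Conclusion.** The concern holds as a conditional bias in an exploratory comparison. Grouping by completed surgery distorts per-woman results if some women conceive while waiting and are then not operated on. On the natural reading, under the assumed inputs above, the null RR is about 0.90 if all planned women try while waiting, 0.97 if a quarter do and 1.00 if none do. It reaches about 0.74 with a 6-month wait and 75% planned for surgery. The distortion runs against surgery for conception and live birth, and in its favour for loss per woman. Loss per pregnancy is about unbiased if risks are equal across women and any waiting-time conception cancels surgery; otherwise it need not be.

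It would go too far to say that the surgery comparison is biased whatever happens, or always to surgery's disadvantage. Neither follows from the documents. The prevalence objective is unaffected. The change is worth making because it is cheap now, and the missing dates may not be recoverable later.

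**What to change.** - **Method of collection of data and outcomes, and Patient Journey:** state the follow-up origin for each cohort, consistently with the flow chart. Collect outcomes from HyCoSy onward for all women with hydrosalpinx, including those later operated on.
- **Data items:** record the surgery date; each conception date (or gestation at outcome, for live births as well as losses); and whether the woman was trying to conceive before surgery.
- **Statistical Analysis:** make loss and live birth per pregnancy the main surgery comparison, classing each pregnancy by whether surgery preceded its conception. For conception, count time trying before surgery as unoperated and time after it as operated, and report this descriptively. Three-month bands since trying began are optional, since the cells will be sparse.
- **Interpretation:** keep the comparison labelled exploratory, and say that some bias may remain if fecundity and loss risk are linked. In a null simulation with loss risk varying from 20% to 60% between women in line with fecundity, classing pregnancies this way still gave a loss RR of 1.00 to 1.13; with a 30% to 50% spread it gave 1.00 to 1.05.

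The cost is wording in three sections, two added self-reported items (conception date and trying status), and up to two extra calls or emails per operated woman. The surgery date is already needed to time post-treatment contacts. Recall will be imperfect, as the protocol itself foresees, and the result stays imprecise. No decision about surgery changes.

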## Accrual and Analysis

### Sample Size

We will attempt to recruit approximately 203 patients. For a prevalence survey in a condition where the prevalence is unknown, but it is not expected to be higher than 25% for obtaining a 95% level of confidence and precision at 0.05 we have estimated that 184 patients are required. To account for up to a 10% level of attrition, 203 patients should be recruited.

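### The sample size of 184 does not give ±5 percentage points with 95% confidence at 25% prevalence: those inputs need 289, and 184 gives about ±6.3 points

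*Protocol*

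**What the plan says.** The calculation is in the protocol under Accrual and Analysis, Sample Size. It gives three inputs and two results.

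- Prevalence: "the prevalence is unknown, but it is not expected to be higher than 25" (per cent).
- Confidence, precision and the resulting number: "for obtaining a 95% level of confidence and precision at 0.05 we have estimated that 184 patients are required".
- Recruitment: "To account for up to a 10% level of attrition, 203 patients should be recruited".

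The section gives no formula, no size for a finite source population, no one-sided bound and no lower planning prevalence. Objective 1 is to establish the prevalence of hydrosalpinx in the recurrent miscarriage population. The Statistical Analysis section commits only to descriptive statistics for that result: "For the prevalence survey of hydrosalpinx in the recurrent miscarriage population data will be presented using descriptive statistics".

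**The concern.** The three inputs are enough to fix the sample size for a single proportion, so the figure can be checked from the text alone. A prevalence of 25% with a 95% interval of ±0.05 needs nearly 300 women, well above 184.

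Prevalence is the first objective, and this is the only calculation offered for the size of the study. It is also the only statement of how precisely the prevalence will be known. If it is wrong, readers will credit the main result with a precision that the design does not have at the one prevalence the protocol names.

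**Working it through.** **Inputs** (all from the Sample Size section): p = 0.25, two-sided 95% confidence so z = 1.96, d = 0.05 read as a half-width, stated n = 184, attrition 10%, recruitment 203.

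**1. Trying to reproduce 184.** The formula is n = z² p(1 − p) / d².

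1.96² × 0.25 × 0.75 / 0.05² = 3.8416 × 0.1875 / 0.0025 = 288.1, so **289**.

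Other methods and readings of the same inputs:

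| Method or reading | n |
|---|---|
| Wilson interval | 286 |
| Clopper-Pearson interval | about 306 |
| Normal approximation with continuity correction | 308 |
| Arcsine (lower or upper side) | 268 or 306 |
| 0.05 read as total width (4 × 288.1 = 1,152.4) | 1,153 |

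None is near 184. The shortfall against 289 is 289 − 184 = 105 women, and 105/289 = 36%.

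**2. What would have to change to reach 184.** Changing one input at a time:

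- Precision: 1.96 × √(0.1875/184) = 0.0626 instead of 0.05.
- Prevalence: p(1 − p) = 184 × 0.0025 / 3.8416 = 0.1197, so p = 13.9% instead of 25%.
- Confidence: z = 0.05 / √(0.1875/184) = 1.566, which is 88.3% instead of 95%.
- Finite-population correction with an assumed N = 500: 288.1 / (1 + 287.1/500) = 183.02, which rounds up to 184.

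Using z = 1.645 (a 90% two-sided interval) gives 202.9, so 203. That equals the recruitment target but not the 184, and it contradicts the stated 95%.

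**3. Precision that the planned numbers give.** Half-width = 1.96 × √(p(1 − p)/n), in percentage points.

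| Prevalence | n needed for ±5 | Half-width, n = 184 | Half-width, n = 203 |
|---|---|---|---|
| 10% | 139 | 4.3 | 4.1 |
| 13.9% | 184 | 5.0 | 4.8 |
| 15% | 196 | 5.2 | 4.9 |
| 20% | 246 | 5.8 | 5.5 |
| 25% | 289 | 6.3 | 6.0 |

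At 25% the Wilson 95% interval for 46/184 runs from 19.3% to 31.7%. Even with no attrition, all 203 women give ±5.96 points at 25%.

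**4. Attrition step.** 184 × 1.10 = 202.4, rounded up to 203, which reproduces the protocol's figure. But 203 × 0.90 = 182.7, just under 184. Dividing by the retained fraction gives 184/0.9 = 204.4, so 205. The gap is two recruits.

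**The case against.** **A hidden assumption rather than a slip.** A finite-population correction with the round figure of 500 gives 184 after rounding up, and recruitment is from one named clinic, so this origin is conceivable. It remains a guess: the protocol states no population size, and Objective 1 is about the recurrent miscarriage population. The inclusion criteria are also described as wide so that prevalence in that population can be assessed. If the correction was used, the section would still have to say so and defend it.

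**25% is a ceiling.** This is fair as far as it goes. The shortfall of 105 applies at the ceiling, shrinks below it and disappears at about 13.9%. But the protocol calls the prevalence unknown and names no other value. Below 50% the variance rises with prevalence, so the ceiling is the value to plan on. The claim fails from about 14% to 25%, which is (25 − 13.9)/25 = 44% of the range allowed.

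**The practical effect is small.** The interval at 25% is about 1.3 points wider on each side than stated, and no test, threshold or stopping rule depends on ±5 points. This stands. It is a reason to correct the statement rather than enlarge the study, but it does not make the statement true.

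**The attrition point is trivial.** This largely stands. The protocol says approximately 203 and up to 10%, and at 9% attrition 203 × 0.91 = 184.7 remain. Prevalence is fixed at the HyCoSy, so for Objective 1 the losses that matter are mainly those between consent and the scan. The conclusion does not rest on this point.

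**Conclusion.** The concern holds. With the protocol's own inputs the requirement is 289 evaluable women, and 184 is 36% below it. At 25% prevalence 184 women give ±6.3 points at 95% confidence, or ±5 points at about 88%. The stated precision is true only for a prevalence of about 13.9% or lower.

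This assumes that 0.05 is the half-width of a two-sided interval for a single proportion, that 25% is the planning value, and that no finite-population correction applies. Reading 0.05 as a total width makes the gap much larger. Changing the interval method moves the requirement only between 268 and 308. The one route found to 184 that keeps all three stated inputs needs a source population of about 500, which the protocol does not state. The attrition slip is real but minor.

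**What to change.** Correct the Sample Size section in one of two ways.

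1. **Keep the size and restate the precision.** Suggested text: *Recruiting 203 women and allowing for 10% attrition leaves about 183 evaluable, which gives a 95% confidence interval of about ±6.3 percentage points if prevalence is 25%, and ±5 points or better if prevalence is about 13.8% or lower.* Check: 1.96 × √(0.1875/183) = 0.0627; for ±0.05, p(1 − p) = 183 × 0.0025 / 3.8416 = 0.1191, so p = 13.8%. This is a wording change with no extra patients. Its only cost is a less favourable stated precision.
2. **Keep ±5 points at 25% and change the size.** This needs 289 evaluable women and 289/0.9 = 321.1, so 322 recruited, which is 322 − 203 = 119 more than planned.

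The first is proportionate, since nothing in the protocol turns on exactly ±5 points. If an unstated assumption such as a finite source population produced 184, it should be stated and reconciled with Objective 1, or dropped.

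In the same edit, inflate for attrition by dividing by 0.9, so that 184 becomes 205 if 184 is kept as a target. It would also help to say that prevalence will be reported with a 95% confidence interval, so that the achieved precision is visible. The Wilson interval is suitable, but the choice of method can be left to the SAP.
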